#### 4.1.1. Data Presentation for the 26-Week RCP

Data summaries for the 26-week RCP will be presented by randomized treatment groups (ie, ravulizumab and placebo).

#### 4.1.2. Data Presentation for the OLE Treatment Period

Data summaries for the OLE Period will be presented by treatment sequence (ie, placebo to ravulizumab and ravulizumab). For participants initially randomized to placebo, Baseline will be redefined as the last measurement taken prior to the first dose of ravulizumab in the OLE Period (eg, dose at Week 26).

#### 4.1.3. Handling of Dropouts or Missing Data

No imputation will be performed for missing baseline values. For postbaseline data, any imputation will be specified in the derivation of the endpoint.

Missing outcome data due to the coronavirus disease 2019 (COVID-19) pandemic (eg, dropout due to COVID-19) is assumed missing-at-random.

Missing data for quality of life (QoL) instruments will be handled as specified in Section 6.3.

The following relevant IEs may occur during the study:

- Receipt of acute therapy with standard DM treatment therapy or prohibited medications
- Treatment discontinuation due to AE, lack of efficacy, or death

The handling of these relevant IEs is detailed in each analysis section.

## 4.2. Primary Analysis

The primary efficacy endpoint analysis will be based on the Randomized Set. Participants will be analyzed based on the randomized arm, regardless of the actual treatment received. The estimand for the primary analysis is defined in Table 2.

Table 2:Estimand for Primary Analysis

Estimand	Treatment	Population	Variable	Relevant Intercurrent Events	Population-Level Summary
Primary analysis	Ravulizumab Placebo	Randomization Set	TIS40 response rate at Week 26	
 
Receipt of acute therapy with standard DM treatment or prohibited medications
 
Treatment discontinuation due to an AE, lack of efficacy, or death during RCP
 
	Difference in the percentage of TIS40 response between ravulizumab and placebo arms

Abbreviations: AE = adverse event; DM = dermatomyositis; RCP = Randomized Controlled Period; TIS40 =Total Improvement Score greater than or equal to 40.

#### 4.2.1. Derivation of Endpoint

The primary endpoint is TIS40 response, defined as an International Myositis Assessment and Clinical Group - Total Improvement Score (IMACS-TIS)  $\geq$  40 at Week 26.

The International Myositis Assessment and Clinical Group (IMACS) developed a consensus on outcome measures and definitions of improvement that should be used in clinical studies for DM (Aggarwal, 2017). The consensus was reached for a joint analysis-based continuous model using absolute percentage change in 6 independent core set measures (CSMs; physician global activity, patient global activity, extramuscular disease activity, muscle strength, Health Assessment Questionnaire [HAQ], and muscle enzyme levels).

The improvement score within each CSM is calculated based on the absolute percentage change from Baseline  $(100 \times [follow-up value - baseline value] / range)$  as shown Table 3. TIS ranges from 0 (worst improvement) to 100 (best improvement) is based on the improvement from Baseline and relative weight of each CSM; TIS will be calculated by summing the improvement scores from Baseline across the 6 CSMs at each Follow-up Visit.

CSM (Range/Units)	Definition of "Improvement" Based on Absolute Percentage Change a	Level of Improvement Based on Absolute Percentage Change	Improvement Score
Physician global	"Improvement" is defined as a	Worsening to 5% improvement	0
activity	decrease, or negative percentage	> 5% to 15% improvement	7.5
(0.0-10.0 cm)	change, in the Physician Global	> 15% to 25% improvement	15
	Activity score	> 25% to 40% improvement	17.5
		> 40% improvement	20
Patient global	"Improvement" is defined as a	Worsening to 5% improvement	0
activity	decrease, or negative percentage	> 5% to 15% improvement	2.5
(0.0-10.0  cm)	change, in the Participant Global	> 15% to 25% improvement	5
	Activity score	> 25% to 40% improvement	7.5
		> 40% improvement	10
Manual muscle	"Improvement" is defined as an	Worsening to 2% improvement	0
testing (MMT-8)	increase, or positive percentage	> 2% to 10% improvement	10
(0-150)	change, in the MMT-8 score	> 10% to 20% improvement	20
		> 20% to 30% improvement	27.5
		> 30% improvement	32.5
HAQ	"Improvement" is defined as a	Worsening to 5% improvement	0
(0-3)	decrease, or negative percentage	> 5% to 15% improvement	5
	change, in the HAQ score	> 15% to 25% improvement	7.5
		> 25% to 40% improvement	7.5
		> 40% improvement	10
Enzyme b,c	"Improvement" is defined as a	Worsening to 5% improvement	0
activity	decrease, or negative percentage	> 5% to 15% improvement	2.5
(enzyme	change, in the enzyme with the most	> 15% to 25% improvement	5
specific d)	abnormal activity level	> 25% to 40% improvement	7.5
		> 40% improvement	7.5
Extramuscular	"Improvement" is defined as a	Worsening to 5% improvement	0
disease activity	decrease, or negative percentage	> 5% to 15% improvement	7.5
(0.0-10.0 cm)	change, in extramuscular disease	> 15% to 25% improvement	12.5
	activity score	> 25% to 40% improvement	15
		> 40% Improvement	20

Table 3:IMACS-TIS Algorithm

- a Absolute percentage change is calculated as follows:  $100 \times \left(\frac{\text{Follow-up value baseline value}}{\text{Parts}}\right)$
- b The muscle enzyme that has the most abnormal serum activity is defined as the enzyme with the highest Baseline level as a percentage of the ULN for the relevant enzyme.
- c The most abnormal muscle enzyme will be selected from the following at Baseline and followed over time: creatine kinase; aldolase; alanine aminotransferase; aspartate aminotransferase; and lactate dehydrogenase.
- d The range for each enzyme will be defined based on a multiple of the ULN for that enzyme as follows: creatinine kinase range =  $15 \times ULN$ ; aldolase range =  $6 \times ULN$ ; alanine aminotransferase, aspartate aminotransferase, and lactate ranges =  $3 \times ULN$ .
- Abbreviation: CSM = core set measure; HAQ = Health Assessment Questionnaire; IMACS-TIS = International Myositis Assessment and Clinical Group - Total Improvement Score; MMT = manual muscle testing; ULN = upper limit of normal

#### 4.2.2. Main Analytical Approach

The primary endpoint measure will be assessed at Week 26 based on the TIS score detailed in Section 4.2.1.

Participants will be defined as a responder at Week 26 if:

- 1. The participant achieves  $TIS \ge 40$  at Week 26 and
- 2. The participant did not have a relevant IE up to and including Week 26 (defined in Section 4.2 and Table 2)

Otherwise, the participant will be counted as a non-responder at Week 26 in the randomized treatment arm.

The proportions of participants with a TIS  $\geq$  40 response at Week 26 in each treatment group with an exact 2-sided 80% CIs using the Clopper-Pearson method will be presented.

The differences in proportions between treatment arms, along with 2-sided 80% confidence intervals (CIs) using Chan and Zhang method (Chan, 1999), will be presented. Barnard's unconditional exact method will be applied to test whether there is a difference in the proportions between the 2 treatment groups.

The analysis as stated above will also be performed at earlier scheduled visits (Weeks 2, 10, and 18), but statistical testing will not be conducted at earlier timepoints. Additionally, a table summarizing the completeness of the TIS values at each scheduled visit will be presented. A listing of participants with an intercurrent event will be also generated.

Plots will be generated to display the proportion of responders (along with 80% exact CIs) by scheduled visit and treatment arm during the RCP.

#### 4.2.3. Sensitivity Analyses

To assess the robustness of the primary endpoint due to the impact of missing data during the RCP, the following sensitivity analysis will be conducted.

The following imputation methods will be performed for missing TIS values in which a relevant IE did not occur up to and including the visit:

Imputation Method         Cases Where Imputation Method Used	
Average of TIS values	• Missing TIS value at Week 10 or 18 where there are observed
	TIS values directly prior to and after the missed visit

Imputation Method	Cases Where Imputation Method Used	
Treatment group mean	• Missing TIS value at Week 2	
	• Missing TIS values at all scheduled visits in the RCP	
Last observation carried forward (LOCF)	
 
Missing TIS values at visits where no adjacent visits with no observed TIS values directly prior to and after the missed visit
 
	

Once the dataset is complete with no missing values of TIS, then TIS will be dichotomized and analyzed using the same manner as described in Section 4.2.2.

## 4.3. Secondary Endpoints

All secondary endpoints will be analyzed using the Randomized Set. There will be no formal testing of the secondary endpoints. Nominal p-values will be presented for endpoints where statistical testing is performed. Handling of the relevant IEs (acute therapy with standard DM treatment/prohibited medications and treatment discontinuation due to AE, lack of efficacy, or death) is described within each of the endpoints.

#### 4.3.1. Total Improvement Score at Week 26

The Total Improvement Score (TIS) at Week 26 will be analyzed using an MMRM. Any data following the relevant IE will be set to missing, and the missing value will be imputed using the LOCF before the relevant IE.

The MMRM will include the observed TIS values at post-Baseline scheduled visits (Weeks 2, 10, 18, and 26) as the dependent variable. The model will include categorical effects of treatment, study visit, and treatment-by-study visit interaction. An unstructured covariance matrix will be used to model the correlations among repeated measurements within each participant. The Kenward-Roger method will be used to estimate the denominator degrees of freedom. If the model using the unstructured correlation matrix fails to converge, then an alternative correlation structure resulting in the best model fit based on the Quasi-likelihood information criterion (QIC) (ie, smallest QIC) will be used among the following correlation structures: autoregressive (1), Toeplitz, and exchangeable.

At each visit, the least square (LS) mean with corresponding standard error and 80% CIs will be displayed by treatment arm. The LS mean treatment difference (ravulizumab - placebo) in TIS at Week 26 will be presented along with the 80% CI along with the corresponding p-value.

Descriptive statistics will also be generated by treatment arm at each scheduled visit.

LS means (± SEM) figure of TIS by treatment arm will be plotted.

#### 4.3.2. Change From Baseline in Cutaneous Dermatomyositis Disease Area and Severity Index Activity Score at Week 26

The Cutaneous Dermatomyositis Disease Area and Severity Index (CDASI) instrument measures activity and damage in the skin while the Clinician or Clinical-Investigator examines the participant. A summary score of Total activity and total damage are collected at each scheduled visit. Any data following the relevant IE will be set to missing, and the missing value will be imputed using the LOCF before the relevant IE.

Change from Baseline in in Total Activity Score at Week 26 will be analyzed using an MMRM. The MMRM model will include the observed Total Activity Score values at post-Baseline visits (Weeks 2, 10, 18, and 26) as the dependent variable. The model will include categorical effects of treatment, study visit, treatment-by-study visit interaction, and adjust for baseline Total Activity Score. An unstructured covariance matrix will be used to model the correlations among repeated measurements within each participant. The Kenward-Roger method will be used to estimate the denominator degrees of freedom. If the model using the unstructured correlation matrix fails to converge, then an alternative correlation structure resulting in the best model fit based on the QIC (ie, smallest QIC) will be used among the following correlation structures: autoregressive (1), Toeplitz, and exchangeable.

At each visit, the LS mean with corresponding standard error and 80% CIs will be displayed by treatment arm. The LS mean treatment difference (ravulizumab - placebo) in the change from Baseline in Total Activity Score at Week 26 will be presented along with the 80% CI and corresponding p-value.

Descriptive statistics of actual values and change from Baseline in Total Activity Score will also be generated by treatment arm at each scheduled visit.

LS mean ( $\pm$  SEM) figures of change from Baseline in Total Activity Score by treatment arm will be plotted.

Summaries of Total Damage Score will be descriptive. actual values and change from Baseline in total damage score will be presented by treatment arm and scheduled visit.

#### 4.3.3. Change From Baseline in 5 IMACS CSMs at Week 26

Change from Baseline in the 5 IMACS Core Set Measures (CSMs) at Week 26 will be analyzed using an MMRM. The 5 IMACS CSMs are comprised of (1) extramuscular disease activity, (2) physician global activity assessment, (3) patient global activity assessment, (4) manual muscle testing (MMT-8), and (5) HAQ. Any data following the relevant IE will be set to missing, and the missing value will be imputed using the LOCF before the relevant IE.

For each of the 5 CSMs, the outcome variable is change from Baseline in CSM at Weeks 2, 10, 18, and 26 and will include fixed effects of treatment arm (ravulizumab, placebo), visits (Weeks 2, 10, 18, and 26), treatment by visit interaction term, and adjustment for baseline of the core set measure. An unstructured covariance matrix will be used to model the correlations among repeated measurements within each participant. The Kenward-Roger approximation will be used to calculate the denominator degrees of freedom. If the model using the unstructured correlation matrix fails to converge, then an alternative correlation structure resulting in best model fit based on the QIC criterion (ie, smallest QIC) will be used among the following correlation structures: autoregressive (1), Toeplitz, and exchangeable.

Within each CSM, the LS mean with corresponding standard error and 80% CIs will be displayed by treatment arm and visit. The LS mean treatment difference (ravulizumab - placebo) in the CSM at Week 26 will be presented along with the 80% CI along with the corresponding p-value.

In addition, change from Baseline in each of the muscle enzymes (sixth CSMs) will be analyzed using the MMRM model as specified above. A separate model for each muscle enzyme (creatine

kinase, aldolase, alanine aminotransferase, aspartate aminotransferase, and lactate dehydrogenase) will be generated.

Descriptive statistics of actual and change from Baseline in the 5 CSM will also be generated by treatment arm at each scheduled visit.

#### 4.3.4. Response Related to Muscle Enzymes - Normalization of Most Abnormal Baseline Enzyme at Week 26

Muscle enzymes are classified as the following 5 laboratory parameters: creatine kinase, aldolase, alanine aminotransferase, aspartate aminotransferase, and lactate dehydrogenase. For each participant, at Baseline, the most abnormal muscle enzyme is the laboratory parameter with the highest ratio (result/ULN) among the 5 laboratory parameters. Normalization of the most abnormal Baseline enzyme will be achieved if the result is less than the ULN (eg, ratio  $\leq 1$ ).

Participants will be defined as a responder at Week 26 if:

- 1. The participant achieves normalization of the most abnormal baseline muscle enzyme (eg, ratio  $\leq$  1) at Week 26 and
- 2. The participant did not have a relevant IE (defined in Section 4.2 and Table 2) up to and including Week 26 and
- 3. The participant did not have normal muscle enzymes at Baseline.

Otherwise, the participant will be counted as a non-responder in the randomized treatment arm.

The proportions of participants with a normalization of the most abnormal muscle enzyme at Week 26 in each treatment group, along with exact 2-sided 80% CIs using the Clopper-Pearson method, will be presented. The differences in proportions between treatment arms, along with 2-sided 80% CIs using the Chan and Zhang method (Chan, 1999), will be presented. Barnard's unconditional exact method will be applied to test whether there is a difference in the proportions between the 2 treatment groups.

The analysis as stated above will also be performed at earlier scheduled visits (Weeks 2, 10, and 18), but statistical testing will not be conducted.

## 4.3.5. CDASI Response (7-Point Improvement) at Week 26

A decrease from Baseline in CDASI Activity Score is considered an improvement.

Participants will be defined as a responder at Week 26 if:

- 1. The participant achieves a decrease from Baseline of at least 7 points or greater at Week 26 and
- 2. The participant did not have a relevant IE (defined in Section 4.2 and Table 2) up to and including Week 26

Otherwise, the participant will be counted as a non-responder in the randomized treatment arm.

The proportions of participants with a CDASI response of 7-point improvement or greater at Week 26 in each treatment group, along with exact 2-sided 80% CIs using the Clopper-Pearson method, will be presented. The differences in proportions between treatment arms, along with 2-sided 80% CIs using the Chan and Zhang method (Chan, 1999), will be presented. Barnard's

unconditional exact method will be applied to test whether there is a difference in the proportions between the 2 treatment groups.

The analysis as stated above will also be performed at earlier scheduled visits (Weeks 2, 10, and 18), but statistical testing will not be conducted.

Plots will be generated to display the proportion of responders (along with 80% CIs) by scheduled visit and treatment arm.

#### 4.3.6. Cutaneous Dermatomyositis Activity Physician's Global Assessment Response (Almost Clear or Clear) at Week 26

The Cutaneous Dermatomyositis Activity Physician's Global Assessment (CDA-IGA) is a scale used to measure disease severity in participants with skin disease. It is a 5-point Likert scale (0=clear, 1=almost clear, 2=mild, 3=moderate, and 4=severe) assigned by the Investigator to describe the overall appearance of lesions at a visit.

Participants will be defined as a responder at Week 26 if:

- 1. The participant response is almost clear or clear at Week 26 and
- 2. The participant did not have a relevant IE (defined in Section 4.2 and Table 2) up to and including Week 26 and
- 3. The participant demonstrated an improvement from Baseline (eg, mild at baseline to almost clear at Week 26 and almost clear at baseline to clear at Week 26).

Otherwise, the participant will be counted as a non-responder in the randomized treatment arm.

The proportions of participants with a CDA-IGA response (almost clear or clear) at Week 26 in each treatment group along with an exact 2-sided 80% CIs using the Clopper-Pearson method will be presented. The differences in proportions between treatment arms, along with 2-sided 80% CIs using Chan and Zhang method (Chan, 1999), will be presented. Barnard's unconditional exact method will be applied to test whether there is a difference in the proportions between the 2 treatment groups.

The analysis as stated above will also be performed at earlier scheduled visits (Weeks 2, 10, and 18), but statistical testing will not be conducted.

## 4.3.7. TIS20 Response at Week 26

A TIS20 response is defined as an IMACS-TIS  $\geq$  20.

Participants will be defined as a responder at Week 26 if:

- 1. The participant achieves  $TIS \ge 20$  at Week 26 and
- 2. The participant did not have a relevant IE up to and including Week 26 (defined in Section 4.2 and Table 2)

Otherwise, the participant will be counted as a nonresponder at Week 26 in the randomized treatment arm.

The analysis method as stated in Section 4.2.2 will be used to assess TIS20 at Week 26.

#### 4.3.8. TIS60 Response at Week 26

A TIS60 response is defined as an IMACS-TIS  $\geq$  60.

Participants will be defined as a responder at Week 26 if:

- 1. The participant achieves  $TIS \ge 60$  at Week 26 and
- 2. The participant did not have a relevant IE up to and including Week 26 (defined in Section 4.2 and Table 2)

Otherwise, the participant will be counted as a nonresponder at Week 26 in the randomized treatment arm.

The analysis method as stated in Section 4.2.2 will be used to assess TIS60 at Week 26.

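### The fallback covariance structure for the Part A mixed models is to be chosen by QIC, a GEE criterion that those models do not produce

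*SAP*

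**What the plan says.** SAP 4.3.1 states the model: "The Total Improvement Score (TIS) at Week 26 will be analyzed using an MMRM". It fixes the first-choice covariance, "An unstructured covariance matrix will be used to model the correlations among repeated measurements within each participant", and the small-sample method, "The Kenward-Roger method will be used to estimate the denominator degrees of freedom". The contingency is "If the model using the unstructured correlation matrix fails to converge, then an alternative correlation structure resulting in the best model fit", with the choice made "based on the Quasi-likelihood information criterion (QIC) (ie, smallest QIC) will be used among the following correlation structures". The candidates are "autoregressive (1), Toeplitz, and exchangeable".

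SAP 4.3.2 (CDASI activity) repeats the rule, "based on the QIC (ie, smallest QIC", and SAP 4.3.3 (five IMACS core set measures) does so again, "best model fit based on the QIC criterion". Section 4.3.3 then applies the same model to each of five muscle enzymes.

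Protocol 9.4.1.1.2 also names a mixed model for the continuous Part A endpoints. The SAP plans no GEE and gives no likelihood-based criterion or fixed order as an alternative. Its one code example, in SAP 6.4, is for the primary endpoint. QIC is listed among the SAP abbreviations.

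**The concern.** A selection rule works only if the fitted model supplies the quantity to be compared. A mixed model fitted by likelihood or REML gives -2 log-likelihood, AIC, AICc and BIC. QIC is built from a quasi-likelihood evaluated under independence plus a penalty based on the robust variance, and both come from a GEE fit. The SAP therefore names a selector that its own model does not yield.

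If an unstructured fit fails, someone must decide what to use in place of QIC. SAP Section 1 has the sponsor unblinded at the primary efficacy analysis, so that decision could be made with results by arm in view. The covariance structure feeds the standard errors, 80% confidence intervals and nominal p-values of whichever model had failed.

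**Working it through.** The plan gives no figure to reproduce. The check has four steps: the reach of the rule, the size of the covariance models, whether a substitute GEE could supply the missing QIC, and whether a likelihood criterion would do the job.

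**1. Reach (SAP 4.3.1 to 4.3.3).** Continuous secondary endpoints: TIS 1 + CDASI activity 1 + core set measures 5 = 7. Additional enzyme models: 5. Total: 7 + 5 = 12 models.

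**2. Covariance parameters with four post-baseline visits (Weeks 2, 10, 18, 26).**
- Unstructured: 4 × 5 / 2 = 10.
- Toeplitz: 4.
- AR(1): 2.
- Exchangeable: 2.

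The SAP specifies no arm-specific covariance, so one matrix is estimated from all of the roughly 36 participants.

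**3. Can a separate GEE stand in?** The TIS mean model contains only treatment, visit and their interaction. With complete data every participant's design matrix has the form (1, t) ⊗ I, where t is the treatment indicator and I the 4 × 4 identity. The working correlation then cancels from both the estimating equation and the sandwich variance. The estimates are the eight arm-by-visit means whatever structure is assumed, and QIC is the same for every structure.

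Simulated data illustrate this. The parameters are assumed, not taken from the documents: 24:12 participants, four visits, AR(1) errors with correlation 0.7 and SD 15, and a modest baseline effect. Each row is one dataset. QIC comes from a Gaussian GEE and AIC from the REML mixed model.

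| Data and mean model | Criterion | AR(1) | Toeplitz | Exchangeable | Largest minus smallest |
|---|---|---|---|---|---|
| Complete, TIS model | QIC | 152.143266 | 152.143266 | 152.143266 | 0 |
| | AIC | 1048.12 | 1051.39 | 1070.25 | 22.13 |
| About 20% monotone dropout, TIS model | QIC | 138.111 | 138.097 | 138.102 | 0.014 |
| | AIC | 953.04 | 956.88 | 971.68 | 18.64 |
| Complete, plus baseline covariate | QIC | 152.974 | 152.879 | 153.367 | 0.49 |
| | AIC | 1063.72 | 1066.83 | 1086.44 | 22.72 |
| About 20% dropout, plus baseline covariate | QIC | 139.070 | 138.848 | 139.389 | 0.54 |
| | AIC | 986.35 | 989.88 | 999.93 | 13.58 |

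The baseline-covariate rows correspond to the mean models of SAP 4.3.2 and 4.3.3. In the first row QIC can be decomposed by hand: 36 × 4 = 144 observations less 8 mean parameters gives a quasi-likelihood term of 136, and the penalty is 152.143266 − 136 = 16.143266 for all three structures. In the other three datasets QIC was smallest for Toeplitz and AIC for AR(1). So a borrowed QIC gives no choice in the first case and, in the others, a choice resting on differences of about half a unit or less.

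**4. Does AICc work?** AICc = AIC + 2d(d + 1)/(n* − d − 1), with d covariance parameters. For the first dataset take n* = 144 − 8 = 136.
- AR(1): 1048.12 + 12/133 = 1048.21.
- Toeplitz: 1051.39 + 40/131 = 1051.70.
- Exchangeable: 1070.25 + 12/133 = 1070.34.

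The structures separate clearly, and all the quantities come from the mixed model itself.

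**The case against.** The strongest reply is that this is one wrong term in a branch that will probably never be used. Much of that stands.

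- **Non-convergence may be rare.** In an illustrative REML simulation of the TIS model (24:12, AR(1) correlation 0.7, SD 15, values floored at 0 and rounded to 2.5), the unstructured fit converged in 40 of 40 datasets with 20% dropout and in 40 of 40 with 40%. Carrying values forward after intercurrent events also fills visits. The parameters are assumed, the software is not SAS, and skewed enzyme data could behave worse, but nothing suggests that failure is to be expected. A reader might infer that 12 placebo participants cannot support 10 parameters. The matrix is pooled across arms, so that count is not the relevant one.
- **Most of the rule is intact.** A reader might infer that prespecification of the continuous endpoints is lost. It is not: the first choice, the trigger and a closed list of three alternatives are fixed, and only the selector is faulty. Any information criterion, AICc included, picks a structure from the data. The difference is that a valid one is named in advance.
- **A QIC can be computed.** That is true from a separate GEE, so the rule is not uncomputable in every sense. But the SAP specifies no such GEE, and its QIC would not describe the mixed model's fit.
- **No decision depends on it.** SAP 4.3 plans no formal testing of secondary endpoints, and SAP 2.1 makes no multiplicity adjustment. Protocol 9.4 keeps Part A data out of Part B's formal testing.

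It is also tempting to read QIC as a remnant of the weighted GEE that the protocol's summary of changes records as removed. The documents do not establish this. The SAP is version 1.0, and the rationale logged for the Part A secondary endpoints concerns binary ones, whereas QIC sits in the continuous models. The mismatch is the same whatever its origin.

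**Conclusion.** The point holds as a minor, conditional defect. In SAP 4.3.1, 4.3.2 and 4.3.3 the criterion for the fallback covariance structure does not belong to the specified model, and nothing elsewhere in the documents corrects it. If an unstructured fit fails, the stated selector cannot be applied to the mixed model, and a replacement would have to be chosen after unblinding from three structures that remain fixed.

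The reach is 7 continuous secondary endpoints and 5 additional enzyme models, each affected only if its own unstructured fit fails. If all converge, no result changes. The primary analysis uses Barnard's exact test and is untouched.

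The mismatch follows from the text and from the definition of QIC. The exact tie for TIS with complete data follows algebraically. The size of the QIC differences in the other cases rests on single simulated datasets under assumed parameters and is illustrative only. The probability of non-convergence in the real data is unknown.

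**What to change.** In SAP 4.3.1, 4.3.2 and 4.3.3, replace QIC with the smallest AICc from REML fits that share identical fixed effects, among the same three structures. Holding the mean model constant makes the REML criteria comparable. State the sample-size definition that the software uses in AICc, and say whether Kenward-Roger also applies to the fallback fit. A prespecified order of the three structures, taking the first that converges, would serve equally well and would remove data-driven selection altogether. Replace or delete the QIC entry in the abbreviation list.

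The cost is a wording change in three sections and one list entry, best made before unblinding. Data collection, sample size, endpoints and study conduct are unaffected.
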